Hypothesis 3. It is hypothesized that IEP quality will moderate intervention effects. Specifically, it is hypothesized that the DRC intervention will be more effective for children with low-quality IEPs as its use will serve to scaffold poorly constructed or incomplete IEP goals/objectives.

Aim 3. Investigate mediators of treatment outcome

Hypothesis 1. As we outline in our logic model below, the fidelity of implementation ([name] et al., 2014), which includes improved positive teacher-child interactions, increased frequency/consistency of feedback, and enhanced home-based contingency management are all thought to be enhanced through the intervention and will mediate improvement in functional domains. These indicators will be investigated individually as mediators as well as jointly.

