IEP Quality. IEP quality will be assessed using a composite rating by study investigators. Prior to quality ratings, IEPs will be de-identified to remove the participant name and information as well as any information about the school or district. Ratings will evaluate the alignment between needs listed in the IEP with goals/objectives stated in the IEP. This will be one way to determine the quality of the IEP document itself – well-written IEPs should have IEPs with close alignment between academic, behavior, and social/emotional needs and the goals to realize improvement (see appendix C for an outline of the coding sheet to be used in the present study; Pariseau, 2011). We will also track which goals are added by consultants to the DRC that were noted as needs by the teacher, but not listed on the IEP. The occurrence of these issues may indicate that the IEP is outdated, poorly constructed, or not reflective of current behavior. These indicators will comprise an IEP quality score investigated as a moderator. Specifically, the score will be calculated as: (Alignment between needs and goals + additional targets added)/overall alignment). A score of 1 would indicate perfect alignment whereas a score below 1 would indicate discrepancy between needs and goals.

Mediators

Three key components of the DRC intervention that are central to our logic model (see figure in the introduction) will be investigated as mediators of treatment outcome. It is expected that relative to the SAU group, the children in the DRC condition will experience a more positive classroom environment, receive more consistent feedback from teachers, and experience more consistent home-based consequences for school behavior. These three variables will each have a partial mediating effect, and the sum total will fully mediate the effect on treatment outcome.

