estimating equations for both the post-test score and mediators. Specifically, a path model will be estimated in which post-test scores are regressed on a dichotomous indicator of treatment, covariates described above (including pre-test scores and moderators), and on three mediators, measured as aggregate variables across the treatment period, including the quality of the classroom environment (ratio of positive to negative comments direct to the target child), consistency of teacher feedback in the classroom and home-based consequences related to school behavior. Moreover, the mediators will be simultaneously regressed on the indicator of treatment. A prototypic model is depicted below. The dashed line from covariates to post-test indicates that this actually refers to a block of variables that are omitted for presentation purposes A formal evaluation of mediation comes from

tests of whether the product of the coefficients relating treatment to mediators and mediators to outcomes (i.e., the indirect effects) differs from 0 (Bollen, 1987; MacKinnon, 2008). Whereas the joint test of the set of product terms (i.e., $a*d = b*e = c*f = 0$) provides an omnibus test of mediation, individual tests of products (i.e., $a*d = 0; b*e = 0; c*f = 0$) informs the contribution of each specific mediator. When combined with information regarding tests of indirect effects, the statistical significance

of the direct effect of treatment on post-test scores informs whether partial (i.e., if the path 't' is statistically significant) or complete (i.e., if the path 't' in the figure is not statistically significant) mediation is present. All tests of mediation will be based on the use of bootstrapped standard errors, which results in better statistical power and avoids having to make potentially unrealistic distributional assumptions about the mediated effect (MacKinnon et al., 2004; Preacher & Hayes, 2008). All mediated effects will be tested using Mplus software which includes facilities for testing individual and compound sets of mediated effects, as well as the use of bootstrapped standard errors (Muthén & Muthén, 2006).

17.2 If applicable, provide a power analysis.

NOTE: This may not apply to certain types of studies, including chart/records reviews, survey studies, or observational studies. This question is asked to elicit whether the investigator has an adequate sample size to achieve the study objectives and justify a conclusion.

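### Aim 3 predicts full mediation by the sum of three indirect effects, but section 17.1 plans neither a test nor an interval for that sum

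*Combined protocol and SAP*

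**What the plan says.** Section 1.2 (Aim 3, Hypothesis 1) commits to both a separate and a combined look at the mediators: "These indicators will be investigated individually as mediators as well as jointly". Section 10.2 (Mediators) gives the combined prediction its content: "These three variables will each have a partial mediating effect, and the sum total will fully mediate the effect on treatment outcome". All three are expected to move in the beneficial direction under DRC.

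Section 17.1 (Aim 3) then sets out three inferences:

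- Joint: the test that a\*d = b\*e = c\*f = 0, which "provides an omnibus test of mediation".
- Individual: a test of each product, which "informs the contribution of each specific mediator".
- Direct path: with the tests of indirect effects in hand, a significant t means partial mediation, and "complete (i.e., if the path 't' in the figure is not statistically significant) mediation is present".

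On method, "All tests of mediation will be based on the use of bootstrapped standard errors". The section adds that Mplus can test compound sets of mediated effects. That describes the software; it does not name an analysis. Section 17.2 claims power above .80 for moderate indirect effects at N = 216. It gives no path sizes and does not say which mediation test the claim covers.

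**The concern.** The joint hypothesis names one signed quantity, a\*d + b\*e + c\*f, and says that it accounts for the whole DRC effect. None of the three planned inferences reports that quantity with its uncertainty. Rejecting the joint null shows that at least one product differs from zero, whatever its sign. The individual tests describe one mediator each. The path-t rule bears on whether anything is left over, but it reaches complete mediation from a failure to reject.

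At stake is what Aim 3 can conclude. A rejected omnibus test together with a non-significant t would be labelled complete mediation, with no statement of how much the mediators carry or how precisely that is known. When several small effects add up as predicted, the joint test may also miss what the sum would detect. Aims 1 and 2 are not affected.

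**Working it through.** **The plan's own figures.** Section 17.2 gives Cohen's d = .50, covariate R² = .45 and power .80. With two-sided alpha .05 (assumed; not stated), N = 4 × (1.960 + 0.842)² × (1 − .45) / .50² = 4 × 7.849 × .55 / .25 = 69.07, so 70 in two equal arms against the stated 71. This reproduces. The Aim 3 claim cannot be reproduced, because moderate is not defined. For one mediator with both standardised paths equal, simulated power at N = 216 with bootstrap standard errors is 10% at 0.14, 44% at 0.20, 86% at 0.26 and 99.9% at 0.39. Power above .80 is therefore plausible for a single product with paths of about 0.26 or more. That says nothing about the sum.

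**Three constraints against one.** The joint null sets three products to zero, so it has 3 degrees of freedom (inferred from the count; the plan does not state it). For three equal, independent effects, both tests have the same noncentrality. Where the 1-df test of the sum has 80% power (noncentrality 7.85), the 3-df test has 64.5%. It needs 10.90 to reach 80%, and 10.90 / 7.85 = 1.39, or 39% more information.

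**At the trial's size.** From the documents: 108 per arm, R² = .45, total DRC effect .50 SD. Assumed: DRC shifts each mediator by .8 SD, residual mediator correlation .3, alpha .05 two-sided, no missing data.

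Hand check for three equal products totalling .167:

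- Each product is .0556, so each mediator-to-outcome path is .0556 / .8 = .0694.
- Within-arm variance explained by the mediators: .0694² × (3 + 6 × .3) = .0231. Residual: .55 − .0231 = .5269.
- With a the vector of three .8 shifts and R the mediator correlation matrix, a′R⁻¹a = 3 × .64 / 1.6 = 1.2.
- Var(sum) = .0231 × 2/108 + (.5269/216) × 1.2 = .00043 + .00293 = .00336, so SE = .058.
- z = .167 / .058 = 2.88, and power = Φ(2.88 − 1.96) = .82.

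Simulated rejection rates (3-df Wald test with bootstrap covariance; percentile interval for the sum):

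| Products | Sum | 3-df test | Test of the sum |
|---|---|---|---|
| three equal | .167 | .59 | .80 to .84 |
| three equal | .25 | .96 | .99 |
| three equal (full mediation) | .50 | 1.00 | 1.00 |
| all on one mediator | .167 | .90 | .80 to .84 |
| +.10, +.10, −.20 | 0 | .99 | .04 |

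In the last row, the planned test of the third product is significantly negative in at least 99.5% of trials, and path t (true value .50) is significant in at least 99.8%.

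A second set of assumptions (uncorrelated mediators, all standardised paths equal) gives, for the 3-df test against the sum, 19% v 63% at 0.14, 51% v 89% at 0.17 and 83% v 99% at 0.20. At 0.26, both exceed 99%.

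**The path-t rule when mediation is half.** Let the sum be .25 and the direct effect .25, with the same assumptions.

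- Each mediator-to-outcome path is .0833 / .8 = .104. Variance explained is .104² × 4.8 = .052, and the residual is .498.
- Adjusting for the mediators inflates the variance of t by 1 + 1.2/4 = 1.3.
- SE(t) = √(.498 × 2/108 × 1.3) = .1095, z = .25 / .1095 = 2.28, power = Φ(.32) = .63.

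So t is non-significant in about 37% of trials by this formula, and in about 36% by simulation. The omnibus test rejects in 96% of trials here, so roughly a third of such trials would be read as complete mediation. The SE of the sum is √(.052 × 2/108 + (.498/216) × 1.2) = .061. An interval centred on .25 would run from about .13 to .37, beside a total effect of .50.

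**The case against.** The strongest reply is that the plan already covers its hypothesis. Full mediation is a claim that no direct effect remains, which is what path t addresses. The partial effect of each mediator is covered by the individual tests. The joint null is a proper test of whether there is any mediation. A sum that differs from zero would not in itself show full mediation: .167 out of .50 would pass and still contradict section 10.2. All of this stands, and it is why the sum has to be read beside the total effect and t. It does not repair an inference to complete mediation that rests only on non-significance.

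It can also be said that the sum is implied, because in a linear path model it equals the total effect minus t, and both are planned. This largely stands for the point estimate, so a reader who infers that the sum goes wholly unestimated goes too far. The subtraction is only approximate across the two analyses, since section 17.2 uses multiple imputation for Aim 1 and full-information maximum likelihood for Aim 3. It also yields no interval.

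Two stronger readings are tempting. A reader might infer that the plan would declare joint success when the indirect effects cancel or run the wrong way. The documents state no such decision rule, and in the cancelling case the planned individual tests and path t show what has happened. A reader might also infer that the 3-df test is simply the weaker test. It is weaker for small, equal, same-direction effects, can be stronger when one mediator dominates, and is no different under the full mediation that section 10.2 predicts. That is a trade-off and gives no ground for demoting the planned test.

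**Conclusion.** The gap holds in a limited form. Section 10.2 states a hypothesis about the sum of the three indirect effects, and section 17.1 plans no test or interval for that sum. The omnibus test answers a different, legitimate question, and the path-t rule reaches complete mediation only through non-significance. With half mediation, that rule would miss the remaining direct effect in about 36% of trials.

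The power difference is secondary: about .59 against .80 to .84 at a total of .167 SD with equal effects, reversed (.90 against .80 to .84) when one mediator carries it all, and nil at .50. All these figures rest on assumed path sizes, mediator correlation and alpha, none of which the documents give. The mismatch between hypothesis and analysis does not depend on them. This is an improvement available at no cost and leaves the efficacy and moderator conclusions untouched.

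**What to change.** In section 17.1, Aim 3, pre-specify the total indirect effect a\*d + b\*e + c\*f, with a percentile bootstrap interval from the resamples already planned, as the analysis of the joint (sum) hypothesis. Report it with its sign, beside the total DRC effect and path t, so that the share carried by the mediators and its uncertainty can be seen. Keep the joint null as the test of any mediation, and keep the three individual product tests.

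The cost is one line of Mplus code and one or two sentences in section 17.1. No new data, participants or model are needed. It should be settled before the Aim 3 analysis, so that the choice of joint analysis does not follow the results.

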The SBTR has been successfully employed as a primary outcome in our Goal 2 project ([name], Vujnovic et al., 2010; see preliminary study 2), along with two other IES-funded projects, one a between-group study of school-wide social and character development programs ([name], P.I., <http://www.sacdprojects.net>), and the other a study designed to investigate the best dose and sequencing of school-based treatments for children with ADHD ([name], P.I., R324B06045). The SBTR observation system has good inter-rater reliability – the mean difference between the observers on total rule violations recorded was 1.8 (SD=2.3; Range=0-12). For the total rule violations variable, the correlation between the two observers was .96 (p < .001), supporting the inter-rater reliability of the observation measure. The SBTR observation system also demonstrated moderate correlation with the DRC recorded by the teacher (r= -.46), suggesting the half-hour observation relates in the expected manner to the DRC completed over an entire school day ([name], Vujnovic, et al., 2009).

The SBTR observations will occur on three separate days in the month of January (before intervention begins) and three separate days in the month of May for each child. Each observation will last for thirty minutes. Time of day and activity will be controlled. Observers will be blind to the child's treatment condition. To ensure the reliability of this measure, 20% of observations will be completed simultaneously with a second observer to allow the calculation of estimates of reliability. Please see the Table in the Treatment Integrity section below for how these observations are independent and distinct from the integrity observations.

Teacher ratings of behavior. Teachers will be administered the following measures during the first two weeks of the month of January and again in May. The following measures will be used as indicators of student outcomes as secondary measures to the primary observational measure.

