Positive Student-Teacher Interactions. The ratio of positive to negative statements issued by the teacher on the SBTR observational measure will be used as an indicator of student-teacher interactions, with classrooms that have a positive environment having a larger number (i.e., more positives than negatives) relative to those that have a negative environment (i.e., fewer positives than negatives). Prior studies have demonstrated this information can be reliably collected (Vujnovic, et al., 2014). Further, these rates of positive to negative statements can be reliably modified based on background behavioral interventions such as the DRC ([name] et al., 2007). This measure will be collected across SAU and DRC groups.

Teacher Feedback for Targeted Behaviors. Observers in the DRC and SAU groups will have a list of the child's DRC/ITBC targets for each of their classroom observations. Observers will record the frequency of targeted behaviors exhibited as well as the number of targeted behaviors that receive appropriate feedback from the teacher. Observers will be blind to treatment condition. This approach to recording targeted behaviors and denoting which were responded to appropriately is part of the SBTR observation system developed by our group and used successfully in a number of school settings ([name] et al., 2010; [name] et al., 2007; Vujnovic, [name], et al., 2014). In this case we will modify the rule violations typically observed to be the individual child's targeted behaviors. The SBTR observation system has good inter-rater reliability: in one study the mean difference between the observers on total number of challenging behaviors was .53 (SD=3.3; Range=0-12). In an early childhood setting, agreement on the appropriate acknowledgement of challenging behavior was .68 ($p < .05$). For the total challenging behaviors variable, the correlation between the two observers was .94 ($p < .001$; [name] et al., 2010), supporting the inter-rater reliability of the observation measure. As a measure of validity, classroom challenging behaviors were negatively correlated with class climate $r = -.45$ (Massetti et al., 2007). The proportion of DRC/ITBC behaviors that were exhibited by the child that received feedback from the teacher will be used as an indicator of teacher monitoring and feedback of IEP goals.

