Fidelity of Teacher Implemented Interventions. Observers will collect information each month (January to May) on teacher responses to student behavior and general classroom management techniques. These observations will include a recording of frequency counts of social reinforcement (e.g., praise statements) as well as commands and negative feedback (i.e., reprimands) directed toward the individual student across the entire school day. These frequency counts will be combined into a ratio of positive to negative statements and used as an indicator of classroom environment. After each observation, observers will also complete a post-observation inventory form. These forms will ask the observer to rate the teacher's use of social reinforcement, commands, tone of voice, and the overall classroom climate on a 7-point Likert scale. An example of this rating to be completed after the observation is in Appendix C.

Integrity of DRC/Targeted Behavior Feedback. Once per month, observers blind to treatment group assignment will spend a full school day in the child's classroom. The observer will be provided a copy of the child's DRC/ITBC and will record a frequency count of the occurrence of each targeted behavior. In addition, targeted behaviors for which the child received specific feedback from the teacher (i.e., were acknowledged; recorded on the DRC/tracking mechanism if appropriate) will also be recorded. This will yield a daily rate of target behavior occurrence, as well as the proportion of targeted behaviors that received appropriate feedback. Observers will also record the latency between the occurrence of a targeted behavior and teacher feedback regarding the behavior using a stop-watch (a decision rule of latency greater than 1 minute will be used to document "no response" to a target behavior).

For children in the DRC group, we will be able to obtain a sample of the proportion of DRC targets appropriately monitored by the teacher with feedback provided. The observer's completed DRC tracking sheet will also be compared to the DRC completed by the teacher to ascertain a sample of the accuracy of the report sent home to the parent each afternoon. This comparison will be made by the investigators/project coordinator to maintain observer blinds.

Integrity of Home Rewards for School Performance. Following each of the all-day school observations (i.e., monthly), SAU/DRC families will be

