Response: We relied on our previous ($N = 63$), randomized study contrasting DRC and SAU conditions in order to compute effect sizes for the proposed study (see Preliminary Study 2). Results from that study indicated an effect size of approximately Cohen $d = .50$ (or larger) across the majority of outcomes considered. The weighted random effects effect size of between groups studies for ADHD such as this one was $.74$; thus we are using a conservative effect size relative to the larger literature ([name] et al., 2009). We also assumed that covariates (most prominently the pre-test score) would explain at least 45% of the observed variation in post-test scores (in the Goal 2 study using comparable covariates 47% of the variance for post-test scores for objective observations and teacher ratings of ADHD was explained by pre-test scores).

Given these assumptions, Aim 1 will have power of $.80$ to detect effects of Cohen $d = .50$ with $N = 71$ participants. In order to estimate power for Aim 2, we assumed treatment effects of Cohen $d = .4$ and $.6$ within moderator groups (e.g., the treatment effect would be Cohen $d = .4$ in intermediate grades compared to Cohen $d = .6$ in primary grades), which, given the sampling plan that balances participants across levels of dichotomous moderators, is consistent with the marginal treatment effect of Cohen $d = .50$ used for Aim 1. In order to detect treatment effects as small as Cohen $d = .40$ (given $R^2 = .45$, as per Aim 1) with power of $.80$, $N = 105$ participants are necessary. Hence, the total sample size needed to power Aim 2 at $.80$ is adequate at $N = 216$ (i.e., 108 participants $\times 2$ levels of moderator). Based on recent work by Fritz and MacKinnon (2007), the proposed total sample size of 216 will provide power of greater than $.80$ to detect moderate sized indirect (mediated) effects (there is no standard metric for reporting effect sizes for indirect effects). We

conclude that N=216 participants results in power of .80 or greater to address all three motivating aims. The use of modern methods for dealing with missing data (Multiple Imputation for Aims 1 and 2, Full Information Maximum Likelihood estimation for Aim 3) ensure that all N = 216 participants will contribute to each analysis.

17.3 Describe any procedures that will be used for quality control of collected data.

Response:

Treatment Integrity and Fidelity of the Consultant Activities

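### Aim 3 would call mediation complete whenever the direct path is not significant, which treats a failure to reject as evidence of no direct effect

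*Combined protocol and SAP*

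**What the plan says.** Section 17.1, Aim 3, plans a path model with "three mediators, measured as aggregate variables across the treatment period". The omnibus test asks whether all three indirect products are zero, and each product is also tested on its own. The plan then combines these tests with the significance of t. A significant t means partial mediation. Otherwise, "complete (i.e., if the path 't' in the figure is not statistically significant) mediation is present".

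Two places state what is expected. In section 1.2 the Aim 3 hypothesis says the indicators "are all thought to be enhanced through the intervention and will mediate improvement in functional domains", with no claim about how much of the effect they carry. Section 10.2, under Mediators, goes further: "These three variables will each have a partial mediating effect, and the sum total will fully mediate the effect on treatment outcome".

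On power, section 17.2 says "the proposed total sample size of 216 will provide power of greater than $.80$ to detect moderate sized indirect (mediated) effects". It gives no power for t. Nowhere does the document define how small t must be to count as negligible.

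**The concern.** Once an indirect effect has been shown, the step from *partial* to *complete* rests only on a non-significant t. A non-significant t can mean that the direct effect is absent, or that it was estimated too imprecisely to detect. The rule does not separate the two, and it rewards imprecision: the noisier the estimate of t, the more often mediation is called complete. Bootstrapped standard errors do not change this. If the Benjamini-Hochberg adjustment in section 17.1 were also applied to t, the stricter threshold would make the label more likely still.

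At stake is a report saying that classroom environment, teacher feedback and home consequences explain the whole effect of the daily report card when part of it runs by another route. That would appear to confirm the joint half of the section 10.2 prediction.

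**Working it through.** **Inputs from the plan.** N = 216, 108 per arm (sections 4.1 and 17.2); total effect d = .50 and covariate R² = .45, so residual variance .55 (section 17.2).

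**Assumptions.** Two-sided alpha .05; three equal mediators; the split between direct and indirect effect; the share of treatment variance that the mediators explain jointly (overlap R²). The document gives none of these.

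**Reproducing a stated figure.** No sample size is tied to t, so the nearest check is Aim 1. Total N = 4 × .55 × (1.960 + .842)² / .50² = 69.1, or 70 with equal arms; a noncentral t calculation gives 72. The plan states 71. A one-sided test would give 56. The residual variance and two-sided .05 therefore fit the plan's own arithmetic.

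**Precision of t.** Code treatment ±.5. Let each mediator shift by a (in residual SDs), with residual correlation ρ between mediators and equal slopes b = (.50 − direct)/(3a). Then:

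- k = 3a² / [4(1 + 2ρ)], and overlap R² = k/(1 + k)
- var(e) = .55 − b²(3 + 6ρ)
- SE(t) = √[4 var(e) / (216(1 − R²))]

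With direct d = .25:

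- Lowest overlap (a = .667, ρ = .3): b = .125, R² = .17, var(e) = .475, SE = .103. The half-width is 1.97 × .103 = .20.
- Highest overlap (a = 2, ρ = 0): b = .042, R² = .75, var(e) = .545, SE = .201. The half-width is 1.97 × .201 = .40; the simulated mean is .39.

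For t alone, .25/.103 = 2.43 against a critical value of 1.97 leaves t non-significant in about .32 of trials. With .25/.201 = 1.24 it is about .76.

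**How often the label would be wrong.** The label also needs an indirect effect, so both conditions were simulated: a 3-df Wald test of the three products on the bootstrap covariance significant, and the percentile bootstrap interval for t including 0 (1,000 trials × 500 resamples; Monte Carlo SE at most .016). Proportion of trials meeting both:

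| ρ = 0: overlap R² | .25 | .43 | .56 | .67 | .75 |
|---|---|---|---|---|---|
| direct d = .25 | .36 | .41 | .35 | .25 | .19 |
| direct d = .30 | .22 | .24 | .22 | .17 | .14 |
| direct d = .35 | .10 | .11 | .10 | .11 | .09 |

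| ρ = .3: overlap R² | .17 | .32 | .45 | .56 | .65 |
|---|---|---|---|---|---|
| direct d = .25 | .32 | .42 | .43 | .34 | .30 |
| direct d = .30 | .20 | .25 | .24 | .23 | .18 |
| direct d = .35 | .09 | .14 | .12 | .12 | .12 |

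Rates fall at high overlap because the indirect test loses power too. A repeat simulation gave about .21 to .44 at direct .25 and .07 to .15 at .35.

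**Adding the individual tests.** If all three products must also be significant, the rate drops to at most about .13 to .17 (the maxima of separate runs) at direct .25, and to near 0 at .35.

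**Dependence on sample size.** With half the effect direct and three independent mediators shifted by .5 or .8 SD, t alone is non-significant in 71–77% of trials at N = 72, 32–46% at N = 216 and 6–17% at N = 432. The true direct effect is the same in each case.

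**Could equivalence be shown instead?** Take an illustrative margin of .20 SD, a true t of 0 and SE = √[4 × .55 / (216(1 − R²))]. Power is 2Φ(.20/SE − 1.645) − 1. At R² = 0, SE = .101 and power is .26; at R² = .2, SE = .113 and power is .10.

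**The case against.** The plan does not read t in isolation. The indirect-effect tests come first, so a non-significant t cannot create mediation where none is shown, and the text says that t informs the label, which is softer than deciding it. Aim 3 is explanatory. All of this stands and limits the consequence. It does not supply a criterion for a negligible t, and the two labels are still defined by significance alone.

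A reader might infer that a false label would confirm the whole section 10.2 prediction. The documents do not support that. The prediction has two halves, and the first, that each mediator carries part of the effect, is tested by the individual products. Requiring all three makes false support much rarer, as shown above, although only equal mediators were examined.

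A reader might also model a single mediator that almost coincides with assignment and obtain larger error rates and wider intervals. The plan fits three mediators together, so such a model is not the planned analysis. Overlap should not be assumed trivial either: section 10.2 expects most school-as-usual families to report no home contingencies, so at least that mediator should separate the arms clearly.

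Finally, it is legitimate to hypothesise full mediation. The fault lies in the decision rule, and section 10.2 need not be reworded.

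**Conclusion.** The concern holds as a point about interpreting Aim 3. As written, section 17.1 turns a failure to reject t = 0 into a positive statement that the mediators carry the whole effect, and at N = 216 the estimate of t is too imprecise to bear it. A half-width of .20 to .39 against a planned total effect of .50 means that a non-significant t can leave a sizeable direct effect open. The error rates are scenarios: they depend on the assumed direct share, overlap and equal mediators, none of which the document fixes. The logical fault does not depend on them.

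It would be wrong to infer that the trial's efficacy conclusion is in doubt. The Aim 1 ANCOVA test does not use the label, and the omnibus and individual indirect-effect tests remain valid as planned.

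**What to change.** In section 17.1, Aim 3, delete the rule that assigns partial or complete mediation by the significance of t. Report each indirect effect, the total indirect effect and t, all with bootstrap 95% confidence intervals. State that a non-significant t will not be read as complete mediation, and that the full-mediation prediction in section 10.2 will be judged from the interval for t. The proportion mediated is optional; it is unstable when the total effect is near zero, so give it only with its interval.

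A formal equivalence test is not a practical substitute at this sample size, given power of .10 to .26 at the illustrative .20 SD margin.

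The cost is a few sentences and a few more reported estimates. Bootstrapping is already planned and no new data are needed. The trial gives up the *complete mediation* label.
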